5.8.3 Premature Discontinuation of Study Treatment (Transition to “Reduced Follow- up” Treatment)

Study treatment will begin at the time of the first dose of induction antibody therapy for an islet transplant. Study treatment may be prematurely discontinued for any subject for any of the following reasons:

- The subject is unwilling or unable to comply with the protocol.
- The investigator believes that the study treatment is no longer in the best interest of the subject.
- The renal allograft is lost and the subject elects to terminate chronic immunosuppression.
- Graft Failure: See Study Definitions and Section 5.8.2.
- An unexpected related SAE. The agent(s) to which the event is attributed will be discontinued.

Subjects who prematurely discontinue study treatment will remain in the study until normal termination, for the purpose of monitoring safety and efficacy parameters and will enter the reduced follow-up schedule outlined in Appendix 2. Data from these subjects will be used in the intent-to-treat analysis.

6. CRITERIA FOR PREMATURE TERMINATION OF THE STUDY

6.1 Participant Withdrawal Criteria

In general, subjects may be prematurely terminated from the study for the following reasons:

1. The subject elects to withdraw consent from all future study activities, including follow- up.
2. The subject is “lost to follow-up” (i.e., no further follow-up is possible because attempts to reestablish contact with the subject have failed).
3. The subject dies.

Subjects meeting the definition for intent-to-treat who prematurely terminate from study treatment will not be replaced. Data from such subjects obtained before withdrawal of consent or before being lost to follow-up will be used in the intent-to-treat analysis. If a subject with functioning transplanted islets chooses to withdraw from the protocol, s/he must be informed of their risk for losing his/her islet graft and becoming sensitized if s/he choose to discontinue immunosuppressive therapy and return to his/her original method of insulin management.

6.2 Study Stopping Rules

6.2.1 Protocol Suspension and Review

Study enrollment at all participating clinical sites will be suspended pending expedited review of all pertinent data by the institutional review board (IRB), and the Data Safety Monitoring Board (DSMB), if any one of the following occurs:

1. The Protocol Chair finds any unexpected fatal or life-threatening AE possibly related to the use of the test therapy.
2. Primary non-function (PNF) occurs in 3 or more consecutive subjects at 2 or more participating clinical sites.
3. There are 4 consecutive study subjects with a c-peptide less than 0.3 ng/mL (on random testing, at baseline and 1-3 hours post-MMTT) at 75 days post-transplant.
4. Any event(s) which in the opinion of the Protocol Chair indicates the need for DSMB review.
5. The DSMB recommends termination of protocol enrollment and further transplants on a study-wide basis based on a review of the data and finding evidence that such action is necessary. Statistical guidelines for terminating the study based on monitoring guidelines are provided later in this study protocol.

After the protocol is placed on hold, no additional transplants within the trial will be performed at any participating clinical site until the DSMB meet either in person or by conference call to review in depth the results and circumstances surrounding the islet functional failure or SAE and determine whether the trial enrollment of new subjects and conduct of additional transplants could be safely resumed.

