1.3 Rationale for Selection of Study Treatment Regimen

1.3.1 Investigational Product: Alpha 1 Antitrypsin (AAT) (GLASSIA)

AAT has been found to have potent anti-inflammatory and immunomodulatory properties in small and large animal studies and has been found to promote islet engraftment and survival in small and large animal experiments. It is approved for use in treating patients with congenital AAT deficiency. GLASSIA will be administered 90 mg/kg IV prior to transplant and the 30mg/kg dose repeated Monday/Wednesday/Friday through day 21 post-transplant.

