5. STUDY TREATMENT REGIMEN

Please refer to Section 1.5 and to applicable package inserts and product labeling for known and potential risks to human subjects associated with the study treatment regimen.

Table 1. Islet Transplant and Immunosuppression Regimen

	Days Relative to Transplant												
	-2	-1	0	1	2	3	4	5	6	7	10	14	21
Islet Transplant			X										
ATG (Initial Transplant Only)	X	X	X	X	X								
Basiliximab (Subsequent Transplants Only)			X				X						
AAT			X										AAT will be given on Monday, Wednesday, Friday schedule for total of 9 doses in 3 weeks
Etanercept			X				X				X	X	

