6.2.2 Site Suspension and Review

Study enrollment and initial islet transplants will be suspended (placed on hold) at a participating clinical site, pending expedited review of all pertinent data by the IRB, and the DSMB, if any one of the following occurs:

1. Any possibly study-related grade 5 AE; or
2. Two SAEs related to the islet transplant procedure (e.g., bleeding, thrombosis, gall bladder injury); or
3. Two consecutive primary non-functioning transplants. See Study Definitions.

After any site is placed on hold, no additional transplants will be performed at that site until the DSMB meet either in person or by conference call to review in depth the results and circumstances surrounding the islet functional failure or SAE and determine whether the trial enrollment of new subjects and conduct of additional transplants could be safely resumed at that site, or whether there could be implications for the continuation of the entire proposed pivotal protocol also at other affiliated sites testing the same protocol.

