8.2.3 Grading and Attribution

GRADING CRITERIA

The study site will grade the severity of AEs experienced by study subjects according to the criteria set forth in the most current version of the *CIT-TCAE*. This document provides a common language to describe levels of severity, to analyze and interpret data, and to articulate the clinical significance of all AEs.

AE severity will be graded on a scale from 1 to 5 according to the following standards in the *CIT-TCAE* manual:

- Grade 1 = Mild AE.
- Grade 2 = Moderate AE.
- Grade 3 = Severe and undesirable AE.
- Grade 4 = Life-threatening or disabling AE.
- Grade 5 = Death.

AEs, not included in the *CIT-TCAE* listing, should be recorded and their severity graded from 1 to 5 according to the General Grade Definition provided below.

Table 5. General Severity Definition of Adverse Event

Grade 1	Mild	Transient or mild discomforts (< 48 hours), no or minimal medical intervention/therapy required, hospitalization not necessary (non-prescription or single-use prescription therapy may be employed to relieve symptoms, e.g., aspirin for simple headache, acetaminophen for post-surgical pain).
Grade 2	Moderate	Mild to moderate limitation in activity some assistance may be needed; no or minimal intervention/therapy required, hospitalization possible.
Grade 3	Severe	Marked limitation in activity, some assistance usually required; medical intervention/therapy required hospitalization possible.
Grade 4	Life-Threatening	Extreme limitation in activity, significant assistance required; significant medical/therapy intervention required hospitalization or hospice care probable.
Grade 5	Death	Death.

All AEs will be reported and graded by the PI or designee whether they are or are not related to disease progression or study treatment.

DEFINITION OF ATTRIBUTION

Attribution will only be determined and collected for serious adverse events.

The relatedness, or attribution, of an AE to islet transplantation, which includes the transplant procedures and/or the islet product, or to the immunosuppression and/or infection prophylaxis will be determined by the site investigator. The site investigator will also record the determination of attribution on the appropriate eCRF and/or SAE report form. The relationship of an AE (attribution of AE) to islet transplantation and/or immunosuppression and/or infection prophylaxis and/or standard diabetes care will be defined by using the descriptors provided below.

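### The safety holds in 6.2.1 and 6.2.2 do not pause GLASSIA in other subjects who are mid-course, and SAE attribution does not name GLASSIA

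*Combined protocol and SAP*

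**What the plan says.** **What a hold stops.** Section 6.2.1 suspends enrollment at all sites and adds that "no additional transplants within the trial will be performed at any participating clinical site until the DSMB meet". The DSMB is then to "determine whether the trial enrollment of new subjects and conduct of additional transplants could be safely resumed". Section 6.2.2 is built the same way for one site.

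**What triggers it.** Item 1 of 6.2.1 reads "The Protocol Chair finds any unexpected fatal or life-threatening AE possibly related to the use of the test therapy". Item 4 of 6.2.1 lets the Protocol Chair call for DSMB review of any other event. Item 1 of 6.2.2 reads "Any possibly study-related grade 5 AE; or", and item 2 of 6.2.2 is two SAEs related to the transplant procedure, with thrombosis among the examples.

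**How long dosing lasts.** Table 1 in section 5 says "AAT will be given on Monday, Wednesday, Friday schedule for total of 9 doses in 3 weeks". Section 1.3.1 has the 30 mg/kg dose "repeated Monday/Wednesday/Friday through day 21 post-transplant". Section 5.1.1 allows 60 mg/kg after a low trough.

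**Who can stop it.** Section 5.8.3 lists reasons why study treatment may be discontinued in a given subject. They include the investigator's view of the subject's best interest. For an unexpected related SAE it says: "The agent(s) to which the event is attributed will be discontinued". Section 5.8.2 has the site PI report other treatment changes that are judged necessary as protocol deviations. Section 11.1 lets the DSMB or IRB withdraw subjects.

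**How relatedness is recorded.** The clause in section 8.2.3 on what SAE relatedness covers, starting from islet transplantation, runs: "which includes the transplant procedures and/or the islet product, or to the immunosuppression and/or infection prophylaxis will be determined by the site investigator". A later sentence in that section adds standard diabetes care. Table 6 grades relatedness to islets, procedure, immunosuppression or infection prophylaxis.

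**The concern.** A hold is meant to limit exposure until the data have been reviewed. Here it limits new exposure only. If GLASSIA is the suspected cause of a death or life-threatening event, a subject transplanted the week before remains scheduled for three doses a week. The hold rule neither pauses those doses nor asks the DSMB whether they may go on, so two sites could act differently on the same report.

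The attribution codes add a second gap. GLASSIA is listed as an investigational agent in 5.1, yet no category in 8.2.3 or Table 6 names it. Read literally, an SAE caused by GLASSIA and by nothing else fits the unrelated code. That could weaken the SAE data that the DSMB sees and the per-subject rule in 5.8.3, which depends on attribution to an agent.

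What is at stake is subject safety and consistent handling across sites. The primary analysis method is not affected.

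**Working it through.** The plan gives no figure to reproduce. The check has two parts: the text, and the scale.

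**Text.** These are the provisions that could pause GLASSIA in a subject other than the one who had the event:

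| Provision | What it does | Pauses dosing in other subjects? |
|---|---|---|
| 6.2.1, 6.2.2 | Stop enrollment and transplants; DSMB decides whether these resume | No mention of dosing |
| 5.8.3 | Per-subject discontinuation; attributed agent stopped | Only by investigator judgement |
| 5.8.1 | Allows modification for complications; names etanercept, basiliximab and ATG as examples | GLASSIA not named; permissive |
| 5.8.2 | Site PI may change treatment and report a deviation | By discretion |
| 8.3.3 | Site to DCC in 24 hours, DCC to sponsor in 2 business days, sponsor informs all investigators | No deadline for the last step; no dosing instruction |
| 11.1 | DSMB or IRB may withdraw subjects | Only once they act |

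None of them pauses dosing automatically.

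**Course length.** I took each of the seven weekdays as the transplant day.
- Nine doses in total (Table 1): the last dose falls on day 17 to 19, mean 18.0.
- Load plus nine further doses (three a week for three weeks, 1.3.1 and 5.1): the last dose falls on day 19 to 21, mean 20.3. I use 21 as the upper limit.

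**Chance that another subject is mid-course.** Inputs: 20 transplanted subjects and 3 years of accrual (Synopsis), so 3 × 365 = 1,095 days. Assumptions: one course each, spread evenly and independently. With 19 other courses of length L:
- P(at least one) = 1 − (1 − L/1095)^19
- L = 18: 1 − (1 − 0.01644)^19 = 27.0%
- L = 21: 1 − (1 − 0.01918)^19 = 30.8%
- Expected number: 19 × 18/1095 = 0.31, and 19 × 21/1095 = 0.36

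**Sensitivity to repeat transplants.** Suppose half the subjects have a second course, which is an assumption. That makes 30 courses over 1,095 + 243 = 1,338 days, because repeat transplants are allowed up to 8 months after the first. The index subject's own courses are removed, leaving 28 or 29.
- 1 − (1 − 18/1338)^28 = 31.6%, and 1 − (1 − 21/1338)^29 = 36.8%
- Expected number: 28 × 18/1338 = 0.38, and 29 × 21/1338 = 0.46

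**Doses due during a review.** The start is a random time within a course, weighted by course length. The review lengths are assumptions, because the plan says only that review is expedited.

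| Review | Mean doses due, 9-dose / 10-dose course | Maximum |
|---|---|---|
| 7 days | 2.61 / 2.66 | 3 |
| 14 days | 4.06 / 4.29 | 6 |

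**Appendix 2.** The reduced schedule that follows discontinuation under 5.8.3 contains no MMTT, and its day 0 is the day treatment is discontinued. A subject who is only paused should therefore stay on Appendix 1.

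**The case against.** The case for leaving the text alone has weight. The graft is already in place, and withholding GLASSIA on a merely possible attribution may cost engraftment. Stopping new exposure and leaving treated recipients to their investigators and the DSMB is a defensible choice. Reports move quickly, review may be by conference call, and a careful investigator would probably pause anyway. Most holds would affect nobody else. All of that stands, and it limits the weight of the point. It does not supply a common rule for the one trigger that points at the test therapy.

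Three stronger readings are tempting, and the documents do not support them.

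- *That the protocol orders dosing to continue, or that nobody may stop it.* It is silent. Sections 5.8.2, 5.8.3 and 11.1 each give someone a way to stop.
- *That stopping GLASSIA costs the subject the day-75 endpoint tests.* The day-75 column in Appendix 2 counts from discontinuation, not from transplant. It is also arguable that a site PI can withhold one agent as a reported deviation under 5.8.2 and leave the subject on Appendix 1. The 5.8.2 sentence sits under an intolerance heading, but its wording is general.
- *That the missing attribution category keeps the hold from triggering.* Item 1 of 6.2.1 rests on the Protocol Chair's judgement about the test therapy, not on a Table 6 code. Because Table 1 lists AAT under a title that includes immunosuppression, some sites may code a GLASSIA event there. So such an SAE could be coded unrelated; the text does not show that it would be.

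**Conclusion.** The point holds as a gap in the hold rule. Sections 6.2.1 and 6.2.2 leave remaining GLASSIA doses in other mid-course subjects to discretion, even after an unexpected fatal or life-threatening event possibly related to the test therapy. The missing GLASSIA category in 8.2.3 and Table 6 is a separate defect of wording.

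The size is modest. In roughly 7 of 10 study-wide holds no other subject would be mid-course under the 20-course assumption, and a single-site hold would affect fewer. The percentages are conditional on a hold occurring, whose probability is not estimated here. They rest on even accrual and, for the dose counts, on assumed review lengths during which nobody uses the existing powers to stop. I read the test therapy as GLASSIA, the agent this trial adds to the CIT-06 regimen; 6.2.1 does not define the term. The Manual of Procedures was not available, but the protocol does not refer to it for dosing during a hold.

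The change is worth making because it is cheap and concerns safety.

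**What to change.** 1. Add to 6.2.1 items 1 and 4 and to 6.2.2 items 1 and 2: *If the Protocol Chair or site investigator considers the event possibly related to GLASSIA, remaining GLASSIA doses are withheld in mid-course subjects (all sites for 6.2.1, the held site for 6.2.2) until the DSMB has met and decided whether dosing may resume. Missed doses are recorded and not made up. This pause is not premature discontinuation under 5.8.3; the subject stays on the Appendix 1 schedule and in the day-75 analysis.*
2. Add GLASSIA as its own attribution category in 8.2.3 and Table 6.
3. Do not add an instruction that GLASSIA continues during other holds; leave those to the investigator and the DSMB. Section 1.5.2 lists increased clotting as a rare serious reaction to GLASSIA, and thrombosis is one of the procedure SAEs that can trigger a site hold.

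The cost is a few sentences and one category in a protocol amendment. The clinical downside is a shortened course with possible loss of engraftment benefit. It would usually fall on no more than one subject, who would miss about 3 doses if review takes 7 days (an assumption).

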6.2.2 Site Suspension and Review

Study enrollment and initial islet transplants will be suspended (placed on hold) at a participating clinical site, pending expedited review of all pertinent data by the IRB, and the DSMB, if any one of the following occurs:

1. Any possibly study-related grade 5 AE; or
2. Two SAEs related to the islet transplant procedure (e.g., bleeding, thrombosis, gall bladder injury); or
3. Two consecutive primary non-functioning transplants. See Study Definitions.

After any site is placed on hold, no additional transplants will be performed at that site until the DSMB meet either in person or by conference call to review in depth the results and circumstances surrounding the islet functional failure or SAE and determine whether the trial enrollment of new subjects and conduct of additional transplants could be safely resumed at that site, or whether there could be implications for the continuation of the entire proposed pivotal protocol also at other affiliated sites testing the same protocol.

7. STUDY PROCEDURES

A detailed description of activities at each study visit is provided in the SOE in Appendix 1.

7.1 Enrollment and Screening

At the screening visit, the screening procedures and diabetes management details will be discussed in lay terms to each potential research subject. If the potential subject remains interested, she/he will review the screening informed consent document with the coordinator, and an investigator will join the discussion and answer any questions. Once satisfied that all questions have been answered, the potential subject will either decline to participate or sign the screening informed consent document. The potential subject will sign an informed consent form before undergoing any screening study procedures. This may occur at a subsequent visit if the potential subject desires, in order to think further about what participation means and/or to consult with family and/or friends. If at any time the suitability of diabetes care is questioned, the potential subject will be referred for further assessment and management.

Once informed consent has been obtained, eligibility will be confirmed through the performance of the screening visit procedures detailed in Appendix 1, SOE, and from additional reports required from each subject's diabetologist and retinologist. A psychosocial evaluation may be requested if either a coordinator or investigator is unsure whether a potential subject may be mentally unfit to undergo the procedure or to determine whether a psychosocial problem may be responsible for the instability of diabetes; such an evaluation would be performed by an experienced transplant social worker and/or psychiatrist.

More than one visit may be necessary to complete all of the screening procedures. Patients who enroll in this trial may have had some of the required screening tests done prior to signing the screening consent document as part of their routine diabetes care or a previous assessment for standard islet and/or pancreas transplantation at the participating sites. Results from assessments completed prior to signing informed consent must be current within the windows stated in the table below.

Table 4. Timeframes for local screening assessments

Local Screening Assessments	Allowable timeframe prior to the date of consent
EBV IgG	No limit. Positive result required for eligibility.
Retinopathy evaluation; Physical exam; Abdominal US; electrocardiogram (ECG); Cardiac Stress Test; TB Test; TSH; Serology; Coagulation; CMV IgG/IgM (if neg), AAT level, IgA antibody level	Within one year
CBC; Chemistry	Within 6 months
CXR	Within 1 month

The screening pregnancy test, first morning spot urine, and blood draws for all laboratory assessments must be done at the study site after informed consent has been signed. Pregnancy and blood transfusion history will be collected and provided to the local lab for Alloantibody analysis. In addition to the protocol required screening assessments, subjects should meet site-specific requirements for transplant.

Once all eligibility criteria (inclusion and exclusion) are met, subjects will be referred to a study

diabetologist for assessment and additional diabetes care if needed, which will be administered per the guidelines in Appendix 3. All subjects will return to the clinic at least quarterly from the time of enrollment.

7.2 Standard Diabetes Management

After completion of the screening assessments confirming eligibility for the study, a subject will undergo 12 months of standard diabetes management by an experienced clinician (see Appendix 3). If a subject received at least 12 months of diabetes management prior to enrollment and experienced at least one episode of severe hypoglycemia during that time, the subject would not be required to receive standard diabetes care while on study as long as they have a Clarke score of 4 or more. A subject is required to return to the study site for clinic visits every 3 months while undergoing routine care and assessment and while on the waitlist. Monthly HbA1c sampling between the required 3 month interval visits may be drawn and assessed locally. Eligibility will be reconfirmed after 4 months and after 12 months of standard diabetes care. All eligibility assessments must be within the windows required for initial study enrollment. Once eligibility has been reconfirmed, a subject will be placed on the wait list. The subject will continue with standard diabetes management while on the wait list.

7.3 Waitlist/Baseline

Waitlist assessments will be repeated at pre-defined intervals as detailed in Appendix 1. Results from repeat assessments done closest to transplantation will be used as the subject's baseline values. During this period when subjects are awaiting their first transplant, CGMS should be completed as time allows. All one-time baseline assessments should be completed on Day -2, whenever possible, but always prior to the start of induction immunosuppression.

As in any other transplant situation, medical conditions that arise (e.g., new serious infections, malignancy, compliance issues, etc.) will automatically trigger a re-evaluation to determine if the subject remains qualified for the protocol. Only qualified subjects may proceed to donor organ matching and transplant.

